The study will use cross-over, randomized, sham controlled, double-blinded design in which 15 participants with subacute or chronic ABI will be assigned to receive either active anodal spinal stimulation, cathodal spinal stimulation, and sham spinal stimulation experiments for the same duration in a random order. In all the experiments participants will receive exoskeleton-assisted training for duration of 1.5 hours. The first 20 minutes of training will be coupled with spinal

stimulation. Treatment will be administered at an intensity of 5 sessions per week for 2 weeks (Please see study HSC-MS-15-0269 PI: [name]).

Pre-screening Procedures: During the pre-screening process, potential subjects with ABI will be contacted by phone from research personnel. The aim and details of the study will be explained in details (reading from a phone script) and information such as demographics, medical history, medications being used, etc. will be gathered. Also ABI subjects will be screened for tsDCS and transcranial magnetic stimulation (TMS) contraindications (attachment 1, attachment 2) and a subgroup of patients (n=5) will be screened for MRI contraindications (attachment 3). The pre-screening will last about 30 minutes and will be performed in a private area. Once this information is collected, the coordinator will consult with the Drs. [name] (PI) and [name] and they will give final approval for the subject to come to The Institute for Rehabilitation and Research Memorial Hermann for the screening procedure.

Screening (Visit 1, duration: One hour): After subject arrives at TIRR a research personnel will meet him/her at the Motor Recovery Laboratory. The details of the study-specific procedures will be reviewed with the subject together. Subject will be screened for inclusion and exclusion criteria. Signed and dated informed consent will be obtained. Demographics, medical history, list of medications will be recorded. If the subject is female in child bearing ages, a urine pregnancy test will be requested. A medication diary will be given to the subject and asked to document all changes in type and dosage of the medication he/she has been using throughout the study. This will allow us to differentiate a potential effect of a change in dosage or type of medication on movement recovery. After subject meets all Inclusion and Exclusion Criteria he/she will be randomly assigned to active, cathodal or sham tsDCS group.

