Portion of assessment sessions will be videotaped and/or photographed. Subjects will be asked to move or manipulate some objects with the arm while a project staff member will record or photograph. Subjects’ consent will be required to perform and photography or videotaping.

Screening, assessment and treatment sessions will be held at the UTHealth Motor Recovery Laboratory at The Institute for Rehabilitation and Research and at UTHealth Medical School, MRI Facility. A total of up to 42 visits are required. Each visit will take about one-and-a-half hour. Schedule of assessments is shown in Table 1.

Table 1. Schedule of assessments for adults with ABI for the first arm of the design. The subjects will undergo same study schedule in second and third treatment arms (See figure 1).

Assessment	Screening	Baseline Assessment	Intervention period											Post-treatment Assessment	Follow-Up Assessment at 1- week	Follow-Up Assessment at 1- Months		
	Day7- to Day1	Day 1	Day 4(±3) to Day 15(±3)											Day 19(±3)	Day 26 (±4)	Day 45 (±5)		
	Visit 1	Visit 2	Visit 3-12											Visit 13	Visit 14	Visit 15		
ICF	X																	
I/E Criteria	X	X																
Randomization	X																	
Demographics	X	X																
Medical History	X	X																
ASIA (motor and sensory score)		X														X	X	X
Modified Ashworth Scale		X														X	X	X
NHPT		X	X	X	X	X	X	X	X	X	X	X	X	X	X	X	X	X
Motor Activity Log		X	X	X	X	X	X	X	X	X	X	X	X	X	X	X	X	X
Grip Strength		X														X	X	X
Pinch Strength		X														X	X	X
JTHFT		X														X	X	X
FMA		X														X	X	X
Exoskeleton Measurement		X														X	X	X
tsDCS			X	X	X	X	X	X	X	X	X	X	X	X	X			
tsDCS related side effects			X	X	X	X	X	X	X	X	X	X	X	X	X			
MRI Scan		X														X		
TMS		X														X	X	X
SSEP		X														X	X	X
EEG		X														X	X	X
Spinal reflex		X														X	X	X
fNRIS		X	X	X	X	X	X	X	X	X	X	X	X	X	X	X	X	X
Adverse Events		X														X	X	X

[figure not shown]

Figure 1. The cross-over design of the study is illustrated. Abbreviations: Post-tx=Post-treatment assessment, EAAT= Exoskeleton -assisted arm training, tsDCS=transcutaneous spinal direct current stimulation, 1 w f/u= 1 week follow-up after the study intervention, 1 m f/u=1 month follow-up assessment after the study intervention.

Specimens to be collected, including frequency and size/amount: None.

5. SUBJECT POPULATION:

Fifteen adults with acquired brain injury (ABI) will be recruited from TIRR Memorial Hermann,

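### The Visit 1 allocation step names one condition rather than a sequence, and no readable text balances the orders, so 15 participants would probably be unbalanced by period with no period term to absorb it

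*Combined protocol and SAP*

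**What the plan says.** Section 4 (Description of Study) sets out the design: "The study will use cross-over, randomized, sham controlled, double-blinded design". It continues that "15 participants with subacute or chronic ABI will be assigned to receive either active anodal spinal stimulation, cathodal spinal stimulation, and sham spinal stimulation", and the sentence ends "sham spinal stimulation experiments for the same duration in a random order". Each person therefore passes through three conditions in three successive arms.

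The operational step comes later in the same section, under Screening (Visit 1): "After subject meets all Inclusion and Exclusion Criteria he/she will be randomly assigned to active, cathodal or sham tsDCS group". It assigns one condition and does not mention arms 2 and 3.

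Table 1 gives the schedule for the first arm and includes a randomisation row at Visit 1. Its caption adds: "The subjects will undergo same study schedule in second and third treatment arms". The text on follow-up makes the month-1 visit the baseline for the next arm. Training is common to all arms: "In all the experiments participants will receive exoskeleton-assisted training for duration of 1.5 hours".

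No readable text gives a list of sequences, a blocking scheme, an allocation ratio or a concealment method. Section 7 (Data Analysis) plans paired t-tests before and after treatment within each group, and a repeated-measures ANOVA for a time by group interaction. Neither contains a period or sequence term. Nothing suggests that time there means anything other than the assessments around one arm.

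**The concern.** The study has to separate the effect of spinal stimulation from that of the training given in every arm. Each arm adds ten training sessions and repeated testing on the same tasks, so the gain made in arm 1 may well differ from the gain made in arm 3. If one condition falls early more often than sham does, some of that difference in gain enters the comparison with sham.

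The Visit 1 sentence is a parallel-group rule inside a cross-over. Staff following it would know a participant's first condition but not how the second and third are chosen. With 15 people, an unrestricted choice leaves real room for uneven placement, and the planned analysis cannot correct for it.

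**Working it through.** **Plan's own figure.** The only design figure is the sample size of 15. It comes with no effect size, SD, power or dropout rate, so it cannot be reproduced. The check below concerns allocation.

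**Inputs.** From Section 4: 15 participants, three conditions, three periods. Assumed, because the documents are silent: each person's order is drawn independently and equally from the six possible orders.

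**1. Chance of exact balance.** Each condition falls 5 times in each period only if the three orders of one 3x3 Latin square are each used 5 - t times and the three orders of the other square t times each, for t = 0 to 5:

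P = Σ 15! / [((5 - t)!)³ (t!)³] / 6¹⁵

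The terms are 756,756 (t = 0 and 5), 94,594,500 (t = 1 and 4) and 756,756,000 (t = 2 and 3). Their sum is 2 × 852,107,256 = 1,704,214,512. Divided by 6¹⁵ = 470,184,984,576 this is 0.0036, or about 0.4%. Some condition falls 7 or more times in a single period with probability 87%.

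**2. Difference in position, anodal minus sham.** Over the six orders it is ±1 in four and ±2 in two, so its variance is (4×1 + 2×4)/6 = 2. The mean over 15 people, D, has expectation 0 and SD √(2/15) = 0.37 periods. Exact enumeration gives median |D| 0.27, 95th percentile 0.73 and P(|D| ≥ 0.5) = 17%.

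**3. Effect on the estimate.** Let the gain drift linearly by g per period. The unadjusted anodal-sham difference is then shifted by D × g: typically 0.27g, and up to 0.73g in 95% of randomisations. With within-person SD 1 for the gain, its standard error over repeated randomisation is √[(2/15)(1 + g²)], which gives 0.37, 0.41, 0.52 and 0.66 for g = 0, 0.5, 1.0 and 1.5. With balanced orders D = 0, and it stays at 0.37 for every g.

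**4. Power.** This was simulated with 6,000 trials per cell, two-sided 5%, and an assumed anodal effect of 1 SD. The unadjusted test is a paired t-test of anodal against sham gains, standing in for the Section 7 comparison. The adjusted test has participant, condition and period.

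| g (SD per period) | Random orders, no period term | Random orders, period term | Balanced, no period term | Balanced, period term |
|---|---|---|---|---|
| 0 | 72% | 72% | 73% | 76% |
| 0.5 | 62% | 72% | 64% | 75% |
| 1.0 | 44% | 72% | 39% | 76% |
| 1.5 | 29% | 71% | 14% | 75% |

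Across simulation runs the 44% entry ranged from 42% to 44%. Type I error is about 5% for random orders, adjusted or not, and for balanced orders with a period term. For balanced orders without a period term it falls to 2.9%, 0.6% and 0.1% at g = 0.5, 1.0 and 1.5. The paired test still counts period differences as noise: at g = 1 it uses a standard error near 0.52 when the true one is 0.37.

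**5. Check of the remedy.** Write A, C and S for the conditions. Square 1 is ACS, CSA, SAC; square 2 is ASC, SCA, CAS. Three copies of one and two of the other make 9 + 6 = 15 people. Each condition is allocated 3 + 2 = 5 times to each period. Within a square each of its three successive pairs occurs twice, so pairs occur 3×2 = 6 or 2×2 = 4 times.

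**The case against.** A reader might infer that order and treatment will be confounded. The documents do not support that. Near-certain imbalance is not confounding: under independent draws, treatment and period are wholly inseparable with probability about 6 in 10 million. The unadjusted contrast has mean bias of about zero, and |D| is below half a period in about 83% of randomisations. A period term alone leaves mean efficiency at 93% (5th percentile 80%). All of this stands.

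A reader might also infer that repeating the schedule in later arms re-randomises people, so that someone could receive one condition twice. That is strained. The design paragraph lists all three conditions, Table 1 is labelled as the first arm's schedule, its Visit 1 column also holds consent, and the month-1 visit is already the next baseline. What remains is that the text never says randomisation happens once.

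Three further points stand as limits:

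- Figure 1, or the companion protocol that Section 4 points to, may show sequences, and a random order is compatible with a balanced list. Independent draws are therefore an assumption. Even so, the Visit 1 sentence would still conflict with the design paragraph.
- Change is measured from each arm's own baseline, which removes the accumulated level. Only a difference in gain between arms matters, and the documents give neither its size nor its direction.
- Once a period term is in the model, balance adds only about 4 percentage points of power.

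**Conclusion.** The point holds as a contradiction in the allocation text together with an avoidable loss of precision. It does not show a biased design. If orders are drawn independently, 15 people will almost certainly be unbalanced by period, and nothing in Section 7 absorbs the resulting shift. The cost depends on a drift that the documents do not quantify. With no drift it is negligible. At an assumed 1 SD per period and an assumed 1 SD effect, power is about 42-44%, against about 75% with balanced orders and a period term.

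It is tempting to conclude that balanced sequences solve the problem whatever model is fitted. They do not. Balance removes the shift from the estimate, but without a period term the test becomes over-conservative, and at a drift of 1 SD per period its power is about 39%, no better than random orders. Both changes are needed, and the period term brings most of the gain in power.

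**What to change.** Replace the Visit 1 sentence with wording such as:

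> Each participant is randomised once, at entry, to one of the six orders of anodal, cathodal and sham stimulation. The concealed allocation list consists of five blocks of three, each block a complete 3x3 Latin square (three blocks of one square and two of the other, in random sequence). There is no further randomisation before the second and third arms.

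Fix the 3:2 split in advance. If the square were drawn afresh for each block, all five blocks would use the same square with probability 2 × (1/2)⁵ = 1/16, and three orders would never be used.

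In Section 7, analyse change from each arm's own baseline in a model with participant, condition and period (three levels). Make Figure 1 and the Table 1 caption agree with the new text.

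The cost is a few sentences and a new list, with no added participants or visits. There are three downsides. The last order in a block can be deduced if the earlier ones become known, so the list should be held by someone outside treatment and assessment. Dropout would disturb the exact balance. Preceding-treatment pairs are only roughly balanced, at 4 or 6 each, because 15 is not a multiple of six.

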Rationale for exoskeleton-assisted training of arm and wrist movements: There is evidence that treatment intensity has a profound effect on motor recovery and the use of robotic exoskeleton devices has potential to automate labor-intensive therapy procedures (Backhus et al., 2010; Sanchez et al., 2006). In this context, rehabilitative robotic exoskeleton devices can deliver high-dosage, high-intensity repetitive training of single joint movements or functional tasks by coordinated multi joint movements and can provide immediate feedback about performance. Our research team at NeuroRecovery Research Center at TIRR /Memorial Hermann, demonstrated that robotic exoskeleton- assisted training can provide positive gains in arm and hand functions in neural recovery ([name] et al., 2011; Kadivar et al., 2011). These observations have been supported by others (Zarrifa et al., 2011; Cortes et al., 2013).

3. PURPOSE OF THE STUDY:

The purposes of this project are: a) to evaluate if adults with chronic acquired brain injury can improve their upper-limb voluntary movement by participating in a therapeutic program that combines non-invasive spine stimulation with exoskeleton-assisted training (E-A training) to investigate neuroanatomical and neurophysiological mechanisms of therapeutic improvement. Our preliminary data and the literature support the model that augmentation of activity in spared corticospinal tract (CST) axons is a critical mechanism of motor improvement, and furthermore that CST activity can be increased by repetitive motor training and by electrical stimulation of the cervical spinal cord. Therefore, our project will address the goals of providing a direct, beneficial impact to persons with acquired brain injury while, at the same time, investigating the mechanisms that result in improved function.

4. DESCRIPTION OF STUDY:

Fifteen patients with weakness on one side of the body due to stroke ABI will receive ten sessions combined treatment of 20 minutes of 2.5 mA anodal, cathodal, and sham tsDCS over cervical spine combined with high intensity exoskeleton-assisted arm training, five days a week, for 2 consecutive weeks.

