relative changes in oxygenated and deoxygenated hemoglobin from the motor cortex of the brain. This in turn will help examine and understand the effects of a combined tsDCS/exoskeleton- assisted arm training treatment upon motor-related brain activity. FNIRS emits near-infrared light (740nm/850nm) into the head and acquires the amount of light returning using a detector positioned 3cm from the light source. It is a portable, non-invasive device similar to EEG and has been used in multiple research studies investigating brain function under various task-oriented settings. One major risk the fNIRS device poses is potential eye damage if the infrared light-emitting diodes (IR LEDs) are shined into an individual's eyes for an extended amount of time. This will be mitigated however by ensuring that the investigator leaves the device powered off before placing it on the user's head. An additional minor risk includes a mild discomfort caused by the tightness of the headband and straps. The investigator will adjust the device to provide optimal comfort to the subject.

Intervention Period (Visit 3-12, duration: one and a half hours per visit): Within one-week following the baseline visit, subjects will receive; 1) active, 2) cathodal or 3) sham tsDCS along with exoskeleton arm training daily (Monday-Friday) for weekdays for over two-weeks. Stimulation will last a total of 20 minutes along with exoskeleton-training will continue for another 75 minutes.

For spinal stimulation direct current will be delivered by a battery-driven direct current stimulator (Soterix Medical, Model 0707-A) connected to a pair of saline-soaked sponge electrodes (7x5cm, 35cm²).

tsDCS: tsDCS active electrode will be placed on the midline of the posterior part of the cervico-thoracic vertebrae, and the neutral electrode will be placed over the shoulder. The stimulus intensity will be set at 2.5 mA and applied over a 20 min period (Cogiamanian et al., 2008; Winkler et al., 2010; Lamy et al., 2012) resulting in a current density of 0.071 mA/cm² and a delivered total charge of 64 mC/ cm². The current will be ramped up to 2.5 mA over a -30 s period and similarly ramped down at the end of stimulation.

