Exoskeleton-assisted training: The side being trained (right vs left arm) will be weaker side of the body. Treatment will be provided by [name], in a dedicated therapy area in the UTHealth Motor Recovery Lab at TIRR-Memorial Hermann. Subjects will individually perform upper-extremity therapy exercises that are supported by the exoskeleton device. Activities that the subjects will be asked to perform will be selected based on the subject's upper-extremity motor function, including elbow flexion-extension, forearm pronation-supination, wrist flexion-extension, and radial-ulnar deviation. The tasks will be repeated multiple times per session for improved performance. Graphic feedback about performance will be given after each attempt in order to maintain motivation. Rest breaks will be given in order to avoid fatigue.

fNIRS: to measure brain activity over the treatment duration at the beginning of each session fNIRS system will be placed over the head of the subject. Brain activity will be recorded during rest (no active movement with the hand) and during movement (performing a motor task with hand).

Safety Assessment:

Questionnaire: At the end of each therapy session, tsDCS side effects questionnaire will be used to monitor any adverse events and study adherence (attachment 3). At the end of each session, the subject will describe any sensations they felt during stimulation and if they feel anything unexpected happened during the study visit. In addition the subject will be asked to rate his/her level of fatigue, pain, and satisfaction with the activities during the session.

Tolerability Assessment: Participants will be asked to rate the cervical spine unpleasantness and discomfort with a subject scale defining the level from “no discomfort at all” to “unbearable discomfort”.

Post-treatment and Follow-Up Assessment (Visit 13-15, duration: one and a half hours): During this period subjects will be asked to come within a-week after they have completed the study, at week-1 and month-1. Month-1 assessment will serve as the baseline assessment of the next treatment arm. Motor functions tests, exoskeleton measures and neurophysiological measurements with SSEP, TMS and fNIRS will be repeated after the treatment, at 1-week and at 3- months follow-up visits. MRI scan will be performed before and after treatment only.

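### Stimulation sensations and side effects are asked about only at session end, 70 to 75 minutes after the current stops, and the cervical-spine tolerability rating has no stated time point

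*Combined protocol and SAP*

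**What the plan says.** All references are to the combined protocol and SAP.

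- **When stimulation occurs.** Section 4 (Description of Study): "In all the experiments participants will receive exoskeleton-assisted training for duration of 1.5 hours", and "The first 20 minutes of training will be coupled with spinal" stimulation. The Intervention Period text has "Stimulation will last a total of 20 minutes along with exoskeleton-training will continue for another 75 minutes", under a heading that reads "Intervention Period (Visit 3-12, duration: one and a half hours per visit").
- **What kind of training.** The opening of Section 4 describes stimulation "combined with high intensity exoskeleton-assisted arm training, five days a week, for 2 consecutive weeks".
- **When the questions are asked.** Section 4, Safety Assessment: "At the end of each therapy session, tsDCS side effects questionnaire will be used to monitor any adverse events and study adherence", and "At the end of each session, the subject will describe any sensations they felt during stimulation". The same paragraph adds a question on unexpected events, and then "the subject will be asked to rate his/her level of fatigue, pain, and satisfaction with the activities during the session".
- **Tolerability.** A separate Tolerability Assessment rates unpleasantness and discomfort at the cervical spine. No time point is given.
- **Sites.** The tsDCS text in Section 4 puts the active electrode over the cervico-thoracic midline and the neutral electrode over the shoulder. Section 8 (Exoskeleton-training) notes that these patients can have shoulder and arm pain.
- **Analysis.** Section 7 says adverse effects are monitored with the questionnaire and states no comparison of side effects between conditions. Its pain and fatigue comparison names no comparator.

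No section schedules a question during stimulation or at its end.

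**The concern.** The question is about one short part of the session and is put after a much longer part that produces sensations of its own. Two things follow. Brief or mild sensations, such as those during the current ramp, must be recalled after more than an hour of exercise. Discomfort present at session end is also harder to assign to a source, and the shoulder is the clearest case because an electrode lies where pain may arise anyway.

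The questionnaire carries much of the per-session safety recording. In Table 1, as extracted, stimulation-related side effects are marked at the intervention visits, while the adverse-events row is marked only at baseline and at Visits 13 to 15. At stake is how well the trial can describe what anodal, cathodal and sham stimulation feel like, and how often they cause side effects.

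**Working it through.** **Inputs.** Training per session is 1.5 h = 90 min, with stimulation in its first 20 min (Section 4). Training after stimulation is 75 min (Intervention Period). Visits 3 to 12 give 10 sessions per condition, and there are three conditions.

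**Step 1: delay from end of current to the question.**
- Section 4 reading: 90 − 20 = 70 min, which is 70/90 = 78% of the session.
- Intervention Period reading: 75 min as written, in a session of 20 + 75 = 95 min, which is 75/95 = 79%.

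**Step 2: consistency of the plan's own figures.** 20 + 75 = 95 min does not fit the stated 90-minute visit. The delay is 70 or 75 min depending on which text is followed, and the point stands on either.

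**Step 3: a second internal check on stimulation time.** Current density is 2.5 mA / 35 cm² = 0.0714 mA/cm², which agrees with the stated 0.071. Over 20 min (1,200 s) the charge is 0.0714 × 1,200 = 85.7 mC/cm², whereas the plan states 64. The stated charge corresponds to 64 / 0.0714 = 896 s, about 15 min. Fifteen minutes of current in a 90-minute session gives a delay of 90 − 15 = 75 min, so the 70 to 75 range is unchanged. No view is taken here on which figure is right; these passages also need to be reconciled.

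**Step 4: delay for sensations at onset.** The current is ramped up over about 30 s at the start. A sensation felt then is asked about some 90 to 95 min later.

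**Step 5: how often.** 10 sessions × 3 conditions = 30 sessions per participant.

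**Step 6: what earlier questioning changes.** At session end the participant has trained for 90 to 95 min, and at the end of stimulation for 20 min. Exercise before the question falls to 20/90 = 22% or 20/95 = 21% of its present amount. It does not fall to zero, because training and stimulation run together.

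These figures give the size of the delay only. The documents do not allow an estimate of how many reports are lost or misattributed.

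**The case against.** Much can be said for the plan as written. The sensation item is worded to the stimulation period, and fatigue, pain and satisfaction are rated separately, so the items are already partly separated. The side-effects form is an attachment that is not available here and may record site, onset or relatedness. Section 8 has every session supervised by staff and provides for reducing or discontinuing sessions if pain or fatigue worsens, and Section 6 lets participants pause at any time. An obvious reaction at minute 20 is therefore likely to be noticed or volunteered. Since training also runs during stimulation, asking earlier does not isolate the effect of the current.

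All of this stands, and it rules out several stronger readings that a reader might infer:

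- *That tolerability as a whole is measured late, or that the questionnaire is the only per-session measure.* The cervical-spine rating is a separate measure. Its timing is unstated, which is a gap, but it is not shown to be late.
- *That stimulation and exercise effects cannot be told apart.* The documents support harder to tell apart, no more.
- *That training causes neck discomfort which mimics stimulation.* The listed exercises are at the elbow, forearm and wrist. Neck pain is mentioned only as an effect of TMS. The shoulder overlap is documented; a neck overlap is not.
- *That the delay pushes the comparison of conditions towards falsely reassuring results.* Training and delay are common to all conditions of the cross-over, so they can dilute a difference but need not bias it. Section 7 does not specify that comparison for side effects in any case.

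What the objection does not remove is the timing itself. Supervision may pick up obvious reactions, but it is not systematic recording of mild or brief ones.

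**Conclusion.** The point holds as a weakness of measurement timing. Sensations and side effects of stimulation are first asked about 70 to 75 minutes after the current stops and after further intensive training, at up to 30 sessions per participant, and the cervical-spine rating has no time point. The likely consequences are blurred absolute rates and some dilution of any active-versus-sham difference, neither of which can be quantified from the documents. Two assumptions carry this: recall of brief sensations worsens over such an interval, and exercise adds sensations of its own. Severity is low. The measures are secondary safety measures, supervision offsets part of the risk, and efficacy inference is not affected. It is worth changing because the change is cheap.

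**What to change.** In Section 4, Safety Assessment:

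1. Ask the items on sensations during stimulation, and take the cervical-spine tolerability rating, immediately after the 20-minute stimulation. Do this in the same way under anodal, cathodal and sham. This also supplies the missing time point.
2. Keep the side-effects questionnaire and the items on pain, fatigue, satisfaction and unexpected events at session end, to catch late effects.

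The sponsor should also reconcile the 90-minute visit with 20 + 75 = 95 minutes, and the stated charge with the stated stimulation time.

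**Cost.** One more form time point and a short pause in training. Assuming one to two minutes, that is 30 × 1 = 30 to 30 × 2 = 60 minutes per participant over all sessions, equally spread across conditions. Staff already supervise the sessions, so none need be added. Table 1 schedules by visit and not within sessions, so it needs no change. The gain is shorter recall and less exercise before the question; the overlap with exercise is reduced, not removed.
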